- Pathologist evaluates all *cavity shave specimens* and records the following on the Pathology Data Collection Tool:
 - i. Presence/absence of carcinoma at or below the *inked outside surface* of all *cavity shave specimens*
 - ii. Presence/absence of carcinoma at or below the *inked inside surface* of all *cavity shave specimens*
 - iii. Presence/absence of non-malignant abnormal cells (e.g. hyperplastic, dysplastic) at or below the *inked inside surface* of all *cavity shave specimens*

If carcinoma is present, record the following additional information on the Pathology Data Collection Tool:

- i. Type(s) of carcinoma (e.g. IDC, ILC, DCIS, if other specify)
- ii. Shortest distance from each *inked surface* (i.e., inside and outside surfaces) to carcinoma

If non-malignant abnormal cells are present, record the following additional information:

- i. Type(s) of abnormal cells (e.g. hyperplastic, dysplastic)
- Pathologist evaluates all tissue biopsies and records the following on the Pathology Data Tool
 - i. Presence/absence of carcinoma anywhere in a given biopsy
 - ii. Presence/absence of non-malignant abnormal cells (e.g. hyperplastic, dysplastic) anywhere in a given biopsy

If carcinoma is present, record the following additional information on the Pathology Data Collection Tool

- i. Type(s) of carcinoma (e.g. IDC, ILC, DCIS, if other specify)
- ii. Shortest distance from the inked surface to carcinoma

If non-malignant abnormal cells are present, record the following additional information:

SBI-CIP 20-002 Rev: v1.8 A prospective multi-center clinical study evaluating the use of PD G 506 A and the Eagle V1.2 Imaging System for the visualization of carcinoma during breast conserving surgery Page: 129 of 157

i. Type(s) of abnormal cells (e.g. hyperplastic, dysplastic)

Follow-up Procedures (Sections 12.5 & 12.7)

- Perform Day 2 follow-up within 24 hours (+24 hours) of the surgery. If participant has been discharged, follow-up may be performed via the telephone.

 Record any AEs in the EDC.
- Perform Week 2 follow-up within 14 days (-4 days) of the surgery, including administration of the post-operative Breast-Q survey.

Record any AEs in the EDC

If no unresolved AE(s), this is the last in-person study visit.

If unresolved AE(s) is present, follow for additional 7 days.

If unresolved SAE(s) is present, follow for additional 30 days.

Record any (S)AE(s) and outcome in the EDC.

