8.3. Minimizing Bias

The following precautions are in place to minimize bias in data collection:

- No personnel involved with the surgical procedure (i.e., *surgeon*, *surgeon's assistant*) will be aware of the participant's randomized treatment assignment nor be present when the participant is provided with the study drug to ingest.
 - o Blinded research personnel will be instructed not to solicit any information from the participant regarding the taste and/or smell of the investigational drug.
- The participant will be blinded to whether they have been randomized to Arm 1 or Arm 2 for the duration of the study.
- The *surgeon* will be blinded to whether a participant has been randomized to Arm 1 or Arm 2 until the time at which the *surgeon* declares the SoC lumpectomy is complete.
- The individual (e.g. pathologist's assistant, pathologist) processing the surgical specimen(s) will be blind to the manner (e.g. SoC vs. *FGR*) by which samples are obtained and the FL status of the samples. This individual will also be blind to the fluorescence

SBI-CIP 20-002 Rev: v1.8 A prospective multi-center clinical study evaluating the use of PD G 506 A and the Eagle V1.2 Imaging System for the visualization of carcinoma during breast conserving surgery	Page: 47 of 157
---	-----------------

- imaging data collected of the bisected/serially sectioned primary specimen during the perioperative procedures.
- The pathologist performing the histopathological evaluation will be blind to the manner (e.g. SoC vs. *FGR*) by which the samples are obtained and the FL status of the samples.
- To ensure FL-imaging does not influence **SoC margin assessment**, intraoperative data collection tools will document the completion of SoC prior to the **surgeon** being given access to any previously acquired FL imaging data and performing additional FL imaging.

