Dissemination of the randomization code will be by sealed, tamper-protected randomization envelopes. Specifically, the 3rd party responsible for dispensing the investigational drug (e.g. pharmacist) will have unblinded access to the electronic database (EDC). Pharmacists will be granted specific EDC permissions that will allow them to see allocation of subjects at their site, to either the study drug, or placebo. When preparing the study drug or placebo for administration 3 hours before the scheduled surgery, the pharmacist will print the Allocation Form off of the EDC. This form will indicate subject ID, allocation to active drug or placebo, date and time of study drug preparation. The pharmacist will place the Allocation Form into an envelope that has been protected from tampering by carbon paper, seal the envelope, and hand it to the study coordinator along with the prepared investigational product for the subject. The study coordinator or a designate (another member of research team staff other than the surgeon or surgeon's assistant), will administer the investigational product and keep subject under observation for 30 minutes, then hand the intact unblinding envelope to the Operating Room staff. Continued monitoring of the patient at hourly intervals following the initial 30-min observation post-administration of the study

carcinoma during breast conserving surgery	SBI-CIP 20-002	Rev: v1.8	A prospective multi-center clinical study evaluating the use of PD G 506 A and the Eagle V1.2 Imaging System for the visualization of carcinoma during breast conserving surgery	Page: 67 of 157
--	-----------------------	--------------	--	-----------------

drug can be done by trained medical personnel (e.g. the patient's nursing staff). The seal will be broken at the end of the SoC lumpectomy procedure (including resection of the primary specimen and any SoC-driven cavity shave specimens) by the *surgeon's assistant* or a designate (another member of the operating room staff) to confirm the participant's allocation, as detailed in Section 12.4.3.

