12.4.2. Standard of Care Intraoperative Procedures

In all participants, the *surgeon* will perform the lumpectomy following best clinical practice. A lumpectomy is defined as a wide local excision of the intact tumor surrounded by a cuff of tumor-free tissue (determined by palpation and visual inspection). This includes the posterior extent of the resection; routinely excising posteriorly down the chest wall should not be performed. Anterior skin should not be routinely removed unless clinically indicated. Tumor involved margins should be revised as separate margins. Separate incisions should be used for the removal of the primary tumor and the axillary surgery except when they coincide anatomically. Curvilinear incision, concentric with the areolar margin, or transverse incisions are recommended over radial incisions. Drains and approximations sutures should not be used in the breast parenchyma.

For participants who are undergoing sentinel lymph node mapping with blue (or green) dye during their BCS, surgeons should avoid injection of blue dye close to the primary tumor bed if feasible. This may help reduce the presence of blue dye in the tumor tissue and surgical cavity where fluorescence assessments will take place. Current studies demonstrate that the location of dye injection distant to the primary tumor bed does not affect the identification of sentinel nodes⁶⁸. Among study patients who are undergoing lymphatic mapping as part of their index BCS, surgeons must comment on the presence or absence of blue (or green) dye at each specimen surface investigated and in the final cavity surfaces.

The *primary specimen* will be palpated/inspected, assessed using intraoperative ultrasound (if applicable) and where indicated (wire localization/guidance) sent for mammography to assess positive margins. Intraoperative pathological assessment of the *primary specimen* (e.g. touch cytology, frozen section, etc.) is not permitted (as defined in the exclusion criteria). Based on the results of visual inspection/palpation/imaging (*SoC margin assessment*), the *surgeon* will decide if additional tissue should be removed (*SoC-driven cavity shave specimens*).

The *surgeon* will remain blinded to all Eagle V1.2 Imaging System assessment data until the SoC lumpectomy procedure (including resection of *SoC-driven cavity shave specimens*) is complete. All excised specimens must be accurately oriented using orientation sutures (or clips).

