12.4.3. Study-Specific Intraoperative Procedures

The *surgeon* and *surgeon's assistant* will perform study-specific imaging using the Eagle V1.2 Imaging System, *FGR*, and *primary specimen* biopsy collection (if applicable) as outlined in **Appendix 2** and described below. Further note, all videos and images will be automatically timestamped and the Eagle V1.2 Imaging System does not have an audio recording function to annotate actions, therefore all relevant actions must be recorded in the Intraoperative Data Collection Tool. Both Part A and Part B of the study will follow these same procedures.

Imaging acquisition using Eagle V1.2 Imaging System of the excised specimens will occur outside the sterile field, using the Dark Imaging Box (DIB). This will allow the *surgeon* to continue with other aspects of the surgical procedure (e.g. lymph node biopsy/dissection, if applicable) while specimen imaging is being performed in real-time.

A second Handheld Fluorescence Camera will be required, as the draped imaging device used to image the final *cavity* must remain in the sterile field until the completion of the procedure. *Note*: all devices used for specimen imaging, including those used outside the sterile field, must be draped within the CSS prior to use. In both scenarios (e.g. imaging inside or outside the sterile field), the excised specimen(s) will be placed on the DIS during imaging.

Immediately following resection of the *primary specimen* and prior to the *surgeon* performing any *SoC margin assessment* (e.g. palpation, specimen radiography and/or intraoperative ultrasound) or collection of any *SoC-driven cavity shave specimens*, the *surgeon's assistant* will perform FL imaging of *primary specimen* inside the DIB.

This is required in order to: (1) minimize the risk of photobleaching in the SoC specimens and surgical cavity while **SoC margin assessment** is performed and (2) ensure blinding of the **surgeon** is maintained until SoC is complete.

To ensure the FL imaging results do not affect the *surgeon's* clinical decision making with regard to *SoC margin assessment*, the FL imaging results will not be viewed by or shared with the *surgeon* at this stage until the *surgeon* has formally declared SoC is complete.

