- The *surgeon's assistant* will collect a FL video of the *primary specimen* moving systematically through each margin of the specimen. During video capture, the *surgeon's assistant* will capture still images of each of the anatomical surfaces of the *primary specimen* and use the device's inbuilt image annotation feature to assign each image an anatomical orientation annotation.
- WL imaging is encouraged if red PpIX fluorescence is detected.

The surgeon will then perform SoC margin assessment and will verbalize their intention to resect SoC-driven cavity shave specimen(s) as well as what margin assessment informed that decision. In cases where SoC-driven cavity shave specimen(s) are indicated (based on white light

SBI-CIP Rev: 20-002 v1.8	A prospective multi-center clinical study evaluating the use of PD G 506 A and the Eagle V1.2 Imaging System for the visualization of carcinoma during breast conserving surgery	Page: 70 of 157
--	--	-----------------

visualization/palpation \pm intraoperative ultrasound and/or specimen radiography) the *surgeon's* assistant will perform FL imaging of all *SoC-driven cavity shave specimen(s)*.

• The surgeon's assistant will collect a FL video of both the inside and outside surfaces of all SoC-driven cavity shave specimen(s). During video capture, the surgeon's assistant will capture still images of each surface of all SoC-driven cavity shave specimen(s) and use the device's inbuilt image annotation feature to assign each image an anatomical orientation annotation. WL imaging is encouraged if red PpIX fluorescence is detected. Cavity shave specimens must have an orientation marker (e.g. suture or clip) placed prior to imaging such that the surface being imaged (e.g. inside surface vs. outside surface) can be identified in the image.

Following *SoC margin assessment* and resection of all indicated *SoC-driven cavity shave specimen(s)* (if any), the *surgeon* will verbalize that the SoC lumpectomy procedure is complete (the time will be recorded in the Intraoperative Data Collection Tool) and will proceed to opening the randomization envelope. The time the randomization envelope is opened will be noted on the Intraoperative Data Collection Tool.

Following the procedure, the *surgeon* and *surgeon's assistant* will electronically sign the Intraoperative Data Collection Tool to acknowledge that the blind was not broken prior to opening of the randomization envelope.

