SBI-CIP 20-002 Rev: v1.8 A prospective multi-center clinical study evaluating the use of PD G 506 A and the Eagle V1.2 Imaging System for the visualization of carcinoma during breast conserving surgery	Page: 122 of 157
---	------------------

Step	Action
	"Do you intend to revise a margin based on SoC margin assessment ?" If 'Yes' – verbalize which margin(s) will be revised and which SoC margin assessment technique informed that decision, proceed to Step 17 If 'No' – proceed to Step 21 Record response on Intraoperative Data Collection Tool.
17	Surgeon revises margin(s) identified in Step 15a. SoC-driven cavity shave specimen(s) is placed in a black/opaque container and moved to the DIB. Note 1: all cavity shave specimens must be marked (e.g. sutured) for orientation purposes as per SoC. Note 2: all cavity shave specimens must be assigned an identifier that indicates from which margin they were resected and whether they are the 1 st , 2 nd , 3 rd , etc. shave resected from that margin. The identifier should not indicate whether the shave specimen was SoC-driven or FL-driven.
18	 Surgeon's assistant acquires FL-video and FL-images of the outside surface and inside of all (if any) SoC-driven cavity shave specimens collected in Step 15a using the DIB. NOTE 1: In cases where a >1 SoC-driven cavity shave specimen is resected for a given anatomical surface (e.g. two lateral SoC-driven cavity shave specimens) FL-video and FL-images of both the inside and outside surface of all shaves for that orientation must be collected.
19	Surgeon verbalizes completion of the SoC lumpectomy procedure *procedures unrelated to the resection of the primary tumor need not be completed at this stage. Record time of completion of SoC lumpectomy in the Intraoperative Data Collection Tool.
20	If Part A – Proceed to Step 21 If Part B, open randomization envelope: Arm 1 (SoC): proceed to Step 29 Arm 2 (SoC + PD G 506 A + Eagle V1.2 Imaging System): proceed to Step 21 Record the time at which the envelope was opened on the Intraoperative Data Collection Tool.
21	Surgeon acquires FL-video and FL-images of all applicable surfaces of the final cavity

SBI-CIP 20-002 Rev: v1.8 A prospective multi-center clinical study evaluating the use of PD G 506 A and the Eagle V1.2 Imaging System for the visualization of carcinoma during breast conserving surgery Page: 123
--

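### Appendix 2 sends patients with no SoC margin revision straight to Step 21, past the SoC-complete declaration (Step 19) and the randomization envelope (Step 20)

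*Combined protocol and SAP*

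**What the plan says.** Appendix 2 lays out Day 1 as numbered steps with branches. After the SoC margin assessment (Steps 15a and 15b), a row asks whether the surgeon intends to revise a margin. Its label is not printed in the available text; by position it is Step 16. Yes goes to Step 17. For No the row reads "If 'No' – proceed to Step 21". Either answer is recorded in the Intraoperative Data Collection Tool. The steps that follow are:

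- Steps 17 and 18: SoC shaves are taken and imaged.
- Step 19: the surgeon declares SoC complete and the time is recorded.
- Step 20: Part A goes to Step 21. In Part B the envelope is opened and the time recorded; Arm 1 goes to Step 29 and Arm 2 to Step 21.
- Step 21: the surgeon images the final cavity. In the next row the surgeon reviews all fluorescence data.

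The body text gives one sequence for all Part B patients:

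- Section 8.3: "intraoperative data collection tools will document the completion of SoC prior to the" surgeon seeing fluorescence data or imaging further.
- Section 12.3: "The seal will be broken at the end of the SoC lumpectomy procedure".
- Section 12.4.2: the surgeon "will remain blinded to all Eagle V1.2 Imaging System assessment data until the SoC lumpectomy procedure" is complete.
- Section 12.4.3, after resection of SoC shaves: "if any), the *surgeon* will verbalize that the SoC lumpectomy procedure is complete", then "the time will be recorded in the Intraoperative Data Collection Tool) and will proceed to opening the randomization envelope". Arm 1 has no imaging or shaves after that.

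Section 12.4.3 opens by having the study-specific procedures performed "if applicable) as outlined in Appendix 2 and described below".

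**The concern.** A patient who needs no SoC shave still has to reach the end of SoC, have that point declared and timed, and have the allocation revealed. The trial uses that checkpoint to separate the SoC result from anything fluorescence imaging may have influenced. It protects the margin status after SoC, which is the starting state for P(1.1) and P(2.1), and it keeps Arm 1 out of imaging and fluorescence-guided resection (FGR).

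On the printed No branch the surgeon moves from the revision decision to cavity imaging and fluorescence review with none of this done. Allocation is never revealed, so an Arm 1 patient enters steps that Step 20 reserves for Arm 2 and Part A.

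**Working it through.** There is no formula to apply. The check follows the step numbers literally and compares each path with the body text.

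**Is Step 21 really the imaging step?** Yes. Step 20 itself sends Part A and Arm 2 to Step 21, and Step 29 is completion of surgery. Only the label 16 is missing from the text, so this is not a PDF artefact.

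**Margin-revision question**

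| Answer | Path |
|---|---|
| Yes | 16 → 17 → 18 → 19 → 20 → Arm 1: 29; Arm 2 or Part A: 21 |
| No, as printed | 16 → 21 |

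- Rows bypassed by No: 17, 18, 19, 20, which is 4.
- Not applicable without an SoC shave: 17 and 18, which is 2.
- Wrongly omitted: 4 − 2 = 2 (Steps 19 and 20). These carry 1 declaration, 2 recorded times and the Arm 1 exit.

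Section 12.4.3 qualifies the SoC shaves with the words that open "if any), the *surgeon* will verbalize that the SoC lumpectomy procedure is complete", so its declaration and envelope steps cover patients with no shave. In Part A there is no envelope, so only Step 19 is lost.

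**No fluorescence-guided shave.** The row just before Step 25 (Step 24 by position) sends these patients to Step 29.

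- Rows bypassed: 25, 26, 27, 28, which is 4.
- Not applicable without such a shave: 25, 26 and 27, which is 3.
- Wrongly omitted: 4 − 3 = 1 (Step 28), which carries the declaration that imaging assessment is complete and the reason for leaving fluorescent tissue.

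Section 12.4.3 asks for the declaration explicitly when no surface is fluorescence-positive, and for the reason when fluorescence remains unresected. Section 15.6.1 repeats that the reason is recorded. Step 23 Note 1 foresees tissue that cannot be shaved, so this branch can be reached with residual fluorescence.

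**Stale references**

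- Step 18 cites Step 15a for shaves that are collected in Step 17.
- Step 30 Note 3 cites Steps 39-40 for weighing, but those are pathology evaluation. Counting back from the printed 39: blocking 38, discharge check 37, fixation 36, grossing and inking 35, weighing 34.
- Step 17 also cites Step 15a. That can stand, because 15a is the margin assessment.

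**What survives on the printed paths**

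- The No response is recorded before Step 21.
- Section 12.4.3 states that "all videos and images will be automatically timestamped", so the cavity-imaging time gives a latest time for the end of SoC.
- The end-of-procedure sign-off refers to the envelope opening, so an unopened envelope should come to light, though only afterwards.
- Arm 1 receives drinking water (Section 10.1.2.5), so drug-induced fluorescence is not expected to drive resection.
- SoC margin histopathology is kept.
- When no fluorescence-guided shave is taken, fluorescence status is already recorded at Steps 22-23. The P(1.1) residual-fluorescence rule uses that status. P(E.20) uses it together with whether a shave was taken. Neither uses the reason.

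**The case against.** The strongest reply is that this is an editorial slip. Sections 8.3, 10.3, 12.3, 12.4.2 and 12.4.3 state the design consistently. Appendix 2 calls itself a summary and refers the reader back to those sections. Amendment 8 removed steps from this table and renumbered it, so a leftover step number is the likeliest cause, although the documents do not prove it. The Intraoperative Data Collection Tool is not among the documents; if it requires the completion and envelope times for every patient, the wrong number may have no effect. Operating-room staff hold the envelope, and surgeons are trained. Once a No is recorded, SoC resection is in effect finished, so Sections 8.3 and 12.4.2 are partly respected.

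Much of this stands as a limit on the harm. It does not remove the contradiction. A summary may leave out detail, but it should not route staff past a required step, and Section 12.4.3 makes the table part of the instructions. The recorded No states an intention about margins; it is not a timed declaration that SoC is complete. Part A training does not rehearse the envelope, because Part A has none.

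On the second branch, it is fair to say that the explicit declaration and the reason belong to different patients: those with no fluorescence, and those with fluorescence left behind. Step 28 serves both, so the correction is the same. The Step 34 label is inferred by counting rows.

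**Conclusion.** The concern holds. Two branches in Appendix 2 conflict with the body text, and the first bypasses the blinding checkpoint for Part B patients who have no SoC shave. It should be fixed.

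The size is structural: 2 required steps are lost on the first branch and 1 on the second, and 2 cross-references are stale. No effect on any estimate, test or sample size is shown. The number of patients affected cannot be derived, because the documents give neither the share with no SoC shave nor how often staff would follow the table over the text. The conclusion rests on reading the printed step numbers literally and on placing two unlabelled rows (16 and 24) by position.

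**What to change.** Reconcile Appendix 2 with Section 12.4.3:

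- Send the No answer on margin revision to Step 19.
- Send the branch with no fluorescence-guided shave to Step 28.
- In Step 18, cite Step 17 as the source of the SoC shaves.
- In Step 30 Note 3, cite the weighing step in the grossing block (Step 34 by count; confirm against the printed table).
- Leave Step 17's reference to Step 15a as it is.

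The cost is two routing numbers and two cross-references in one table, with no new procedure or data item. Any site worksheet built from the table, and the Intraoperative Data Collection Tool, should be checked for the same routing.
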